### Study Summary

Title	 Ga-DOTATATE PET/CT Assessment of Cardiac Sarcoidosis
Study Design	Prospective study of 15 consecutive patients with suspected or newly diagnosed cardiac sarcoidosis (CS) who are referred for a clinically indicated  FDG (and  NH 3 ) PET/CT scan for cardiac sarcoidosis (CS) will be approached to undergo a  Ga-DOTATATE PET/CT scan. Comparison will then be made between the  Ga-DOTATATE PET/CT and the  FDG and  NH 3 PET/CT to determine if  Ga-DOTATATE detects CS.
Study Center(s)	Mayo Clinic, Rochester MN Campus
Primary Objective	To determine if  Ga-DOTATATE PET/CT will have a similar accuracy as  FDG and  NH 3 PET/CT in diagnosing CS and if it will be able to do so without the need for complex patient dietary preparation that is required with  FDG PET/CT.
Number of Subjects	15 consecutive patients
Main Inclusion Criteria and Diagnosis	Primary inclusion criteria are 1) patients over the age of 18 years of age who are referred for clinically indicated  FDG and  NH 3 PET/CT for cardiac sarcoidosis (CS) 2) have clinically suspected, or newly diagnosed CS 3) are not-pregnant or nursing 4) consent to undergo a  Ga-DOTATATE PET/CT scan.  Diagnosis of CS by  Ga-DOTATATE will be determined by the presence or absence of myocardial uptake of  Ga-DOTATATE using similar methodology as previously reported (1,2).
Study Product, Dose, Route, Regimen, Duration	5.4 mCi of  Ga-DOTATATE will be administered by intravenous route. 60 minutes following administration, a low-dose transmission CT thorax scan will be performed for attenuation purposes followed by a cardiac PET emission scan obtained in the three-dimensional list mode.

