#### 1.2.1.5 Cardiac Experience

There are three critical components to support feasibility of the proposed project: 1) Clinically indicated FDG PET/CT (performed with NH3 PET/CT as the standard of care) is already being performed at Mayo Clinic Rochester routinely with an average 4-5 studies per week and preliminary data have been presented at national meetings based upon these studies, (19) (20) 2) The use of Ga-DOTATATE to image CS is predicated upon sound scientific reasoning, and 3) There are initial reports that Ga-DOTATATE may in fact be able to image CS.

- 1) FDG PET/CT can detect CS but is imperfect: PET/CT/ has proven to have the highest diagnostic accuracy for the detection of CS (10) with a reported sensitivity of 89% (10) and specificity as high as 97% (21). However, these results are predicated upon sufficient dietary preparation. Unfortunately, dietary preparation is often inadequate (11). Indeed, in our own MCR patient population, one-fifth of patients had suboptimal dietary preparation which ultimately compromised image quality and test accuracy (19). As a result, multiple efforts have been undertaken to enhance dietary preparation for FDG PET/CT CS imaging (12-15). Despite these ongoing efforts, there remains no uniform means for dietary preparation. Furthermore, these preparation procedures are onerous and include strict fasting, specific diet adherence and potentially the use of heparin. This is likely the reason for poor compliance with dietary preparations (16). It also requires extra nuclear laboratory personnel time to contact patients and instruct them regarding the dietary procedures. For patients with diabetes mellitus, additional coordination must be made with the Department of Endocrinology. Given these issues, further efforts are warranted to identify another means by which to accurately image patients with known or suspected CS.

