## 2 Study Objectives

To determine if Ga-DOTATATE PET/CT imaging will have a similar accuracy as FDG PET/CT with NH3 in diagnosing CS and if it will be able to do so without the need for complex patient dietary preparation that is required with FDG PET/CT.

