### **3.1 Study Endpoints**

1. Assess utilizing both qualitative and quantitative methods the myocardial Ga-DOTATATE uptake in patients with and without active CS as determined by FDG and NH3 PET/CT.
2. Determine the concordance and discordance of Ga-DOTATATE with FDG and NH3 PET/CT for the presence or absence of CS utilizing FDG and NH3 PET/CT as the “gold-standard” for CS. Determine the sensitivity and specificity of Ga-DOTATATE for the detection of CS will be determined.
3. Calculate physician confidence in study interpretation for both Ga-DOTATATE and FDG and NH3 PET/CT.
4. Compare patient satisfaction between the FDG and NH3 PET/CT and Ga-DOTATATE protocols.
5. Utilize information obtained from the current pilot as a foundation to pursue potentially larger trials.

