#### 7.1.2 Efficacy Analysis

##### 7.1.2.1 Analysis of Primary Efficacy Endpoint

Nominal continuous variables will be represented as the mean +/- SD and categorical variables will be noted as the number and percentage of total. Pearson chi-square test will be utilized to determine statistical significance for continuous variables whereas a Student's two-sample t-test will be implemented to determine statistical significance for continuous variables. Univariate and

multivariate analyses will be performed when relevant. Statistical significance will be set a priori as a p-value less than 0.05. Concordance and discordance of Ga-DOTATATE with FDG and NH3 PET/CT for the presence or absence of CS will be calculated and utilizing FDG PET/CT as the “gold-standard” for CS, the sensitivity and specificity of Ga-DOTATATE for the detection of CS will be determined. Given that this is a pilot study no power calculation will be performed. All statistical analyses will be performed using JMP Pro 9 (SAS Institute INC. Cary, North Carolina).

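### The planned sensitivity and specificity of DOTATATE for CS are percent agreement with FDG/NH3 PET/CT, so they cannot answer an objective about accuracy

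*Combined protocol and SAP*

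**What the plan says.** The Study Summary asks whether DOTATATE "PET/CT will have a similar accuracy as" FDG and NH3 PET/CT in diagnosing CS, and Section 2 repeats this ("imaging will have a similar accuracy as"). Both add the question of avoiding dietary preparation.

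The analysis in Section 7.1.2.1 has two parts. Concordance and discordance of DOTATATE with FDG and NH3 "PET/CT for the presence or absence of CS will be calculated and utilizing" FDG "PET/CT as the “gold-standard” for CS, the sensitivity and specificity of" DOTATATE will be determined. The Statistical Methodology entry of the Study Summary and endpoint 2 of Section 3.1 ("Determine the sensitivity and specificity of" DOTATATE) say the same, except that they name FDG and NH3 together as the reference, where Section 7.1.2.1 names FDG alone. Endpoint 1 compares uptake "in patients with and without active CS as determined by" FDG/NH3 PET/CT, so it too takes the comparator as truth.

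Section 1.2.1.5 says of FDG that it "PET/CT can detect CS but is imperfect". It reports 89% sensitivity and, at best, 97% specificity, both conditional on adequate dietary preparation, and says that preparation was suboptimal in one-fifth of the site's own patients. Under Section 6.1.2 each scan ends in one of three calls: positive, negative or inconclusive. Section 1.1 puts inconclusive FDG scans at up to 30%.

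**The concern.** A test cannot be compared for accuracy with a second test that also serves as the truth. FDG/NH3 then has 100% sensitivity and specificity by construction, and DOTATATE can at best tie. Each conclusive FDG error that DOTATATE avoids is charged to DOTATATE, and each error that both make is credited as correct.

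Nothing else in the plan fills the gap. The adjudication in Section 6.1.2 settles disagreement between the two readers, not between the two scans. Clinical data from the record are to be correlated with SUVmax and are not used as a reference.

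The figures would be reported as sensitivity and specificity for CS, read as accuracy, and carried into the larger study that Sections 3 and 3.1 foresee. Inconclusive reads are a second gap: a 2x2 calculation has no cell for them. The missing-data rule in Section 7 does not help, because an inconclusive read is a recorded result.

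**Working it through.** The plan gives no figure to reproduce: the 15 patients have no stated derivation, and Section 7.1.2.1 says that no power calculation is made. The check is therefore what the planned figures would show in known situations.

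**Inputs.** FDG sensitivity Se = 0.89 and specificity Sp = 0.97 (Section 1.2.1.5; the two come from different sources, and 0.97 is a best value). N = 15 (Section 3). CS prevalence p is not given; 0.3, 0.5 and 0.7 are assumed. All reads are taken as conclusive at first.

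**Formulas.** FDG-positive share P = p·Se + (1−p)(1−Sp), and FDG-negative share is 1−P. FDG error rate e = p(1−Se) + (1−p)(1−Sp).

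(a) Error-free DOTATATE: shown sensitivity = p·Se/P; shown specificity = (1−p)·Sp/(1−P); discordance = e. At p = 0.5: P = 0.445 + 0.015 = 0.460; 0.445/0.460 = 96.7%; 0.485/0.540 = 89.8%; e = 0.055 + 0.015 = 0.070, and 15 × 0.070 = 1.05.

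(b) DOTATATE exactly as accurate as FDG, errors independent given disease status: shown sensitivity = [p·Se² + (1−p)(1−Sp)²]/P; shown specificity = [p(1−Se)² + (1−p)Sp²]/(1−P); discordance = 2p·Se(1−Se) + 2(1−p)Sp(1−Sp).

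(c) DOTATATE exactly as accurate as FDG, all errors shared: 100%/100%, no discordance.

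| Prevalence | (a) shown sens/spec | (a) discordant in 15 | (b) shown sens/spec | (b) discordant in 15 | (c) |
|---|---|---|---|---|---|
| 30% | 92.7%/95.4% | 0.8 | 82.7%/93.0% | 1.5 | 100%/100%, 0 |
| 50% | 96.7%/89.8% | 1.05 | 86.2%/88.2% | 1.9 | 100%/100%, 0 |
| 70% | 98.6%/79.1% | 1.3 | 87.8%/79.0% | 2.3 | 100%/100%, 0 |

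A scan no better than FDG can thus show more discordance (b) or less (c) than an error-free one (a). Shared errors are plausible here, because one NH3 map and the same two readers serve both scans (Sections 6.1.1 and 6.1.2). If FDG specificity were 80% (assumed), case (a) becomes 65.6%/94.4%, 81.7%/87.9% and 91.2%/75.7%, with 2.6, 2.3 and 2.1 discordant.

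**Chance in 15 patients.** The values in (a) are expectations. The probability that an error-free scan meets no FDG error is (1−e)^15: 0.946^15 = 43%, 0.930^15 = 34% and 0.914^15 = 26%. With FDG specificity at 80% it is 6% to 11%.

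**What discordance can say.** Let d be the discordance rate. For binary reads, d is the share where only DOTATATE is right plus the share where only FDG is right; the accuracy difference is the difference of these two shares.
- Upper bound: the absolute accuracy difference cannot exceed d. Exact (Clopper-Pearson) two-sided 95% upper limits for d are 21.8% at 0/15, 31.9% at 1/15 and 40.5% at 2/15.
- Lower bound, with an external FDG error rate: DOTATATE alone can be right in at most e of patients, so FDG accuracy minus DOTATATE accuracy is at least d − 2e. At 89%/97%, 2e = 10.8%, 14.0% and 17.2%. The exact lower limit for d at 7/15 is 21.3%, above all three. With FDG specificity at 80%, 2e = 34.6%, 31.0% and 27.4%; 10/15 (lower limit 38.4%) exceeds all three.

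**Inconclusive reads.** If 20% (assumed from the one-fifth with suboptimal preparation) to 30% (Section 1.1) of FDG reads are inconclusive, 3 to 4.5 of 15 drop out and about 10 to 12 remain. The upper limit with no discordance is then 26.5% (0/12) to 30.8% (0/10).

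**Precision.** With 7 FDG-positive and 8 FDG-negative patients (illustration), complete agreement has exact 95% intervals of 59.0% to 100% and 63.1% to 100%.

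**The case against.** The strongest defence is that the choice is open. The reference is named beside the calculation, gold standard is put in quotation marks, concordance comes first, FDG's limits are stated, and this is a feasibility pilot. No clean alternative exists either: Section 1.1 puts the sensitivity of biopsy as low as 20%. Section 7 lists all subject data and Section 3 plans a chart review of all 15 patients, so discordant cases would be visible.

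Much of this stands. Concordance is a legitimate pilot endpoint, as are reader confidence and patient preference, and no new reference standard is called for. But disclosure does not turn agreement into accuracy, pilot status excuses a missing power calculation and not a mislabelled quantity, and a general listing does not specify any review of discordant scans.

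The objection also sets limits on what may be claimed:
- A reader might infer that an error-free DOTATATE scan must show less than 100%. That holds on average only; at 89%/97% it would show full agreement in about 26% to 43% of such trials.
- A reader might infer that the analysis could never count against similarity. With the protocol's FDG accuracy as an external input, very high discordance (7/15 or more) would indicate lower DOTATATE accuracy.
- A reader might treat the one-fifth with poor preparation as wrong FDG reads. The documents do not separate wrong from inconclusive. Reads called inconclusive and dropped would reduce the misclassification, at the price of a smaller sample.
- A reader might take the 19-patient pilot in Section 1.2.1.5 as showing that DOTATATE outperforms FDG. The title of that reference (number 2) names DOTANOC, so it is context only.

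**Conclusion.** The concern holds in this form. The planned sensitivity and specificity are positive and negative percent agreement with FDG/NH3 PET/CT. That follows from the text and needs no assumption. The trial's own data cannot attribute discordance to either scan or show that DOTATATE is better. Low discordance supports similarity only within a wide bound (21.8% at best with 15 conclusive pairs), and only very high discordance joined to an outside FDG error rate would speak against it.

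The size of the distortion rests on assumed prevalence, on FDG at 89%/97%, on conclusive reads and, in (b) and (c), on how far errors are shared. At 70% prevalence an error-free scan and a merely equal one with independent errors show almost the same specificity (79.1% and 79.0%), while a scan that copies FDG's errors looks best. The point should be settled before the results are analysed, because the primary analysis does not estimate what the objective asks.

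**What to change.** 1. In the Study Summary and Sections 2, 3.1 (endpoint 2) and 7.1.2.1, restate the objective as agreement with FDG/NH3 PET/CT. Report positive, negative and overall percent agreement with exact 95% confidence intervals in place of sensitivity and specificity for CS. Claim no more on accuracy than the discordance rate and its exact upper limit allow. In the same edit, reconcile Section 7.1.2.1 (FDG alone as reference) with the Study Summary and Section 3.1 (FDG and NH3).
2. Report a 3x3 table of positive, negative and inconclusive for each scan, with inconclusive reads kept as their own row and column.
3. After the blinded reads are final, list discordant and inconclusive patients descriptively, with information already in the chart, such as any histology, cardiac MRI, clinical criteria and dietary preparation. The chart review in Section 3 can supply this, though preparation adequacy is not a listed data item and may be missing for some.

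The cost is an amendment submitted to the IRB (Section 10), a little more tabulation, and a pilot that claims agreement rather than accuracy. No new reference standard, reader or procedure is needed.

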### 3 Study Design

The proposed investigation is a feasibility study designed to assess the efficacy of Ga-DOTATATE PET/CT imaging in the CS population. We propose imaging 15 consecutive patients initially (with an intention to do a larger study) with the standard of care approach of both FDG and NH3 PET/CT and a research Ga-DOTATATE PET/CT. The study group will include adult patients who undergo assessment in Mayo Clinic's CS clinic and have suspected or newly diagnosed CS based upon clinical evaluation. A typical proposed timeline of events for each patient processed through the study is as follows (note exact timeline may vary based on patient appointment schedule):

- 1) *Up to 4-6 weeks prior to visit:* Patient charts will be reviewed prior to their initial appointment in the CS clinic. After review, the physician head of the CS clinic (LB) will refer candidates that have clinically suspected (7), or newly diagnosed CS and who will be referred for a clinically indicated FDG and NH3 PET/CT to the primary investigator (JB). JB or other designated staff will contact the potential study candidates via phone or email (using a phone/email script) to determine their potential interest in the study. If the patient expresses an interest in the study, a consent form will be sent in advance for their review. Patients may consent remotely if they choose or can also be consented in-person. Potential study subjects will also be notified that they will be contacted during their visit for participation in the study.
- 2) *Day 1:* During their FDG and NH3 PET/CT assessment, potential study candidates who have not been consented will be approached by the study coordinator to inquire about their participation in the study. If the patient meets all criteria and agrees to participate in the study, then written consent will be obtained at that time.

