#### 6.1.2 Analysis of PET data

Once the cardiac PET/CT images are obtained they will be assessed for the presence of CS utilizing similar methodologies which were previously published (1,2,24).

Qualitative assessment of FDG and NH3 PET/CT and Ga-DOTATATE for each study subject will be made by two different study investigators (JB and AK) who will be blinded to the patient clinical history, laboratory data and any other imaging assessment (including the corresponding CS study-i.e. when reading the Ga-DOTATATE study investigators will be blinded to the FDG results and vice versa) at the time of interpretation. For both FDG and Ga-DOTATATE cardiac uptake study investigators will classify the patient into one of four categories of radionuclide uptake: none, diffuse, focal, and focal on diffuse or diffuse. The portions of the myocardium that demonstrate uptake will be documented in accordance with the 17 segment American Heart Association model (28). In concordance with national guidelines(24), FDG and Ga-DOTATATE examinations will be interpreted simultaneously with NH3 to allow for assessment of myocardial perfusion. Both FDG and Ga-DOTATATE studies will then be labeled as positive for CS, negative for CS or inconclusive.

Any discordance between the findings of the two investigators in regards to the presence or absence of CS as well as the extent will be reviewed by additional investigators (GJ or PC) and final determination in regards to classification of the patient will be made.

Semiquantitative determination of radionuclide uptake will be determined by using commercially available software to calculate maximum standard uptake value (SUVmax) of FDG and Ga-DOTATATE in the heart. This data will be correlated with patient clinical data obtained from the medical record.

The two study investigators (JB and AK) who are reviewing all studies will rank their confidence level for interpretation for each scan on a 5 point scale (1=least confident, 5= most confident). Results will then be compared between the two study modalities.

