## 7 Statistical Plan

### General Considerations

**Continuous data** (e.g., age) will be summarized using the following descriptive summary statistics: the number of subjects (n), mean, SD, median, minimum value (min), and maximum value (max). For each continuous variable, the corresponding mean, median, minimum and maximum will be presented to 1 decimal place and the SD to 2 decimal places, unless otherwise specified.

**Categorical variables** (e.g., qualitative presence of absence of Ga-DOTATATE) will be summarized using counts and percentages. Percentages will be presented to 1 decimal place. Summaries of continuous and categorical data will be presented, as appropriate.

**Incomplete/Missing data:** Missing data (e.g., dates, post-baseline values) will not be imputed, unless otherwise specified; i.e., all missing values and missing post-baseline values will remain as missing in all statistical analyses and listings, unless otherwise specified.

**Outliers:** No formal statistical analyses will be performed to detect and/or remedy the presence of statistical outliers.

Additionally, all subject data, including derived variables, will be presented in subject data listings; listings will display all subjects who were randomized or enrolled in the study.

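### The objective asks whether accuracy is similar, but concordance, sensitivity and specificity are planned as counts and percentages only, with no confidence interval and no definition of similar

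*Combined protocol and SAP*

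**What the plan says.** Section 2 (Study Objectives) asks whether 68Ga-DOTATATE "PET/CT imaging will have a similar accuracy as" FDG PET/CT with 13NH3. The Study Summary gives the same primary objective. Neither place supplies a margin, a threshold or any other meaning for similar.

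The analysis is in section 7.1.2.1, repeated in substance under Statistical Methodology in the Study Summary. Concordance and discordance are to be calculated, with FDG PET/CT as the reference standard, and sensitivity and specificity "for the detection of CS will be determined. Given that this is a pilot study no power calculation will be performed". Under General Considerations in section 7, categorical variables "will be summarized using counts and percentages. Percentages will be presented to 1 decimal place". The only inferential threshold is "Statistical significance will be set a priori as a p-value less than 0.05", which follows the sentences on the chi-square test and the t-test.

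On size and purpose, section 3 says "We propose imaging 15 consecutive patients initially (with an intention to do a larger study". The last endpoint in section 3.1 is "Utilize information obtained from the current pilot as a foundation to pursue potentially larger trials". No section mentions a confidence interval, a standard error or a target precision.

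**The concern.** The objective is worded as a determination about comparative accuracy, while the analysis meant to serve it is purely descriptive. Nothing connects the two: no interval shows how far the data could be from the truth, and no criterion says what result would count as similar or not similar.

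With 15 patients this matters, because a very favourable-looking percentage is compatible with a much poorer test. Sensitivity and specificity are more exposed still, since each uses only the FDG-positive or only the FDG-negative patients. A report could follow the plan to the letter, print a high percentage to one decimal, and leave readers to take it as an answer to the stated objective. The pilot is also meant to inform larger work, so its readers need to see how little precision it carries.

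**Working it through.** **No figure to reproduce.** The sample size of 15 has no power, margin or precision calculation behind it (section 7.1.2.1: "Given that this is a pilot study no power calculation will be performed"). The check is therefore what 15 patients can show.

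**Inputs from the documents.** N = 15 (section 3). Reported FDG sensitivity 89% and suboptimal preparation in one-fifth of the site's patients (section 1.2.1.5). Inconclusive FDG scans in up to 30% (section 1.1). Both kinds of "studies will then be labeled as positive for CS, negative for CS or inconclusive" (section 6.1.2). Withdrawn subjects are not replaced (section 4.3.1).

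**Assumptions.** The FDG-positive/FDG-negative split is not stated; 5 and 10 are used as an illustration. The plan does not say whether inconclusive scans leave the two-by-two table. If they do, 15 × 0.30 = 4.5 would be lost at the upper figure, leaving 10 to 11. If the one-fifth with poor preparation were lost, 15 × 0.20 = 3, leaving 12.

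**Method.** Exact (Clopper-Pearson) two-sided 95% limits for x of n: the lower limit is the 0.025 quantile of Beta(x, n − x + 1) and the upper limit is the 0.975 quantile of Beta(x + 1, n − x). When x = n, the lower limit reduces to 0.025^(1/n). For 15/15 this is 0.025^(1/15) = 0.782; for 5/5 it is 0.025^(1/5) = 0.478. Wilson limits serve as a check.

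| Result | Percentage | Exact 95% CI | Wilson 95% CI |
|---|---|---|---|
| Concordance 15/15 | 100.0 | 78.2–100 | 79.6–100 |
| Concordance 14/15 | 93.3 | 68.1–99.8 | 70.2–98.8 |
| Concordance 13/15 | 86.7 | 59.5–98.3 | 62.1–96.3 |
| 12/12 (12 evaluable, assumed) | 100.0 | 73.5–100 | 75.8–100 |
| 10/10 (10 evaluable, or a class of 10, assumed) | 100.0 | 69.2–100 | 72.2–100 |
| 5/5 (class of 5, assumed) | 100.0 | 47.8–100 | 56.6–100 |
| 4/5 (class of 5, assumed) | 80.0 | 28.4–99.5 | 37.6–96.4 |

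**How easily a good result arises by chance.** If true concordance is 80%, the probability of 14/15 or better is 15 × 0.8^14 × 0.2 + 0.8^15 = 0.132 + 0.035 = 0.167. If true sensitivity is 70%, 5/5 occurs with probability 0.7^5 = 0.168; if it is 80%, 0.8^5 = 0.328.

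**What would be needed.** For a perfect result to have an exact lower limit of at least L, n must be at least ln(0.025)/ln(L). For L = 0.80 this is 16.5, so 17 patients in that class. For L = 0.89, the FDG sensitivity that the protocol cites (used here only for scale), it is 31.7, so 32. Both exceed the whole study.

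**The case against.** The strongest reply is that this is a declared feasibility pilot with descriptive aims. No power calculation is claimed, the verbs attached to the accuracy measures are descriptive, and intervals can be added from the locked data at any time without loss. Nothing about enrolment, imaging or reading would change, and no estimate is biased by the omission. This stands as an argument about severity. It excuses the missing power calculation, but not an objective that asks for more than the analysis can give.

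Four stronger readings are tempting, and the documents do not support them.

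- A reader might infer that only bare percentages will be shown. In fact counts are planned alongside percentages, and section 7 promises subject listings, so a reader could derive intervals. What is missing is the interval itself.
- A reader might infer that the report will declare similarity. No section states a rule for doing so; the plan leaves that conclusion open and does not commit to it.
- A reader might take the 0.05 threshold to govern these measures. It is attached to the chi-square and t-tests, and no test of concordance, sensitivity or specificity is described.
- A reader might infer that the point estimate will be the planning value for the next trial. Section 3.1 speaks only of information as a foundation for larger trials.

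It is also fair to say that an interval alone would not make the objective answerable. With FDG PET/CT as the reference standard, sensitivity and specificity measure agreement with FDG, not which scan is more accurate. That is a reason to reword the objective as well.

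**Conclusion.** The concern holds as a mismatch between objective and analysis. Fifteen patients, reported descriptively, cannot establish similar accuracy: the best possible concordance result still leaves true concordance as low as 78.2%, and one discordant patient lowers that limit to 68.1%. These two figures need only the stated sample size and the assumption that all 15 patients have a conclusive result on both scans. The figures for sensitivity and specificity, such as 47.8% for 5/5, depend on an assumed split, and those for 10 to 12 evaluable patients depend on an assumed handling of inconclusive scans. Wilson limits lead to the same conclusion.

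This is a should-fix. The pilot label, the counts already planned and the absence of any rule for declaring similarity keep it below a fault that must be corrected before the study can proceed.

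**What to change.** In section 7.1.2.1 and under Statistical Methodology in the Study Summary, state that concordance, sensitivity and specificity will each be reported as n/N with a 95% confidence interval, and name the method (Clopper-Pearson or Wilson).

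In section 2 and the Study Summary, reword the accuracy part of the objective as: *to estimate the agreement of 68Ga-DOTATATE PET/CT with 18FDG/13NH3 PET/CT*. Add a sentence that similarity will not be concluded from this pilot's point estimates.

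The cost is wording only: no extra patients, scans or data. The one downside is a less favourable-looking headline, since a figure such as 100.0% would appear beside its interval.
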